The Advertising and Recruitment Cores are responsible for recruiting potential participants for clinical trials from a population that includes a wide range of people of various ages, ethnic backgrounds and with varying degrees of health. Pennington Biomedical has a team of full-time employees dedicated to the recruitment and initial screening of clinical trials. Potential subjects will be identified via a large database of previous study participants along with the use of web, print, and media advertising. The Recruitment and Advertising Cores create and implement individualized, trial-specific advertising and awareness campaigns, including mass media, traditional advertising, and novel methods including social media, digital and email marketing. All advertising and awareness are approved by our on-site IRB to ensure ethical and disclosure standards are met. The PBRC database will also be utilized to find potential subjects for this study.

Study Timelines

Participants will come in for a screening visit. Then approximately a week (~ 7 days) later, participants will come in their Week 0 (baseline) study visit and be provided with ~1 week (~7

days) of food provision. This visit will occur based on self-reported luteal phase of menstrual cycle in women. Next, at approximately 1 week (~day 7), participants will return to the center for an adherence visit and further provision of study foods (Week 1). At approximately 2 weeks (~day 14), participants will return to the center for an adherence visit and further provision of study foods (Week 2). At approximately 3 weeks (~day 21), participants will return to the center for an adherence visit and further provision of study foods (Week 3). Finally, participants will come for their Week 4 assessment and adherence visit. Thus, participation will last approximately 5-6 weeks in total.

Study Endpoints

Study Design: A randomized parallel arm design trial examining solid sugar vs. SSB treatments will be performed. The primary study endpoints are feasibility and change in body weight.

Procedures Involved

Overview:

Participants will arrive at the center following a minimum 10 hour fast. They will undergo anthropometric measurements, psychological and behavioral questionnaires, and fMRI.

Table 1. Schedule of Procedures

| Visit Assessments | Screening Visit | Intervention Period | | | | |
|--|-----------------|---------------------|--------|--------|--------|--------|

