| | | Week 0 | Week 1 | Week 2 | Week 3 | Week 4 |
| Informed Consent | X | | | | | |
| Anthropometrics (height, body weight) | X | | | | | |
| Anthropometrics (body weight, waist and hip circumference, and bioelectrical impedance) | | X | | | | X |
| Brief Lifestyle Interview and non-quantified food record | X | | | | | |
| Contact and Demographic Information | X | | | | | |
| Food Taste Test | X | | | | | |
| Food Craving Inventory (FCI), Yale Food Addiction Survey (YFAS) , Liking and Wanting Procedure, Retrospective Visual Analogue Scales (RVAS) , Barratt Impulsiveness Scale, Delayed Discounting Task, and Food Familiarity and Liking Procedure | | X | | | | X |
| Urine Pregnancy Test | | X | | | | X |
| fMRI (fasting and fed state) | | X | | | | X |
| Randomization | | X | | | | |
| Study Product Dispensed | | X | X | X | X | |
| Adherence check/calculations (self-report and container return), provision of study foods | | | X | X | X | X |

Dose: The energy content of food provision in the SSB and solid groups will be 240 kcal/day. Participants are to consume 1 unit per day of the study.

Diet: Participants will receive no instructions for other dietary modifications; i.e., they will not be told to modify what or how much other food they consume.

Food Acceptability Form: Participants will be asked to rate the study foods for appearance, odor, flavor, texture, sweetness, and overall acceptability at screening. Each participant will be asked to circle the number from 1-9 for each of the characteristics after consuming the study foods.

Psychological Assessments:

Food Craving Inventory (FCI). The FCI^{9,10} is a 28-item measure of specific food craving. The FCI assesses the frequency with which an individual experiences a craving for a particular food. The measure consists of 4 empirically-derived factors: High fats, Sweets, Carbohydrates/starches, and Fast food fats. All items are scored in a 1 (Never) to 5 (Always) multiple choice format. The measure has been shown to be reliable and support has been found all aspects of validity.

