- MRI/fMRI – fasting and fed state
- Treatment consumption – fed state fMRI
- 1 week supply of study product dispensed

Week 1: About 30 minutes – Non-Fasting

- Adherence check
- 1 week supply of study product dispensed

Week 2: About 30 minutes – Non-Fasting

- Adherence check
- 1 week supply of study product dispensed

Week 3: About 30 minutes – Non-Fasting

- Adherence check
- 1 week supply of study product dispensed

Week 4: About 4 hours – Fasting (nothing to eat or drink other than water for at least 10 hours prior to visit) after at least 7 hours of rest the previous evening

This visit will take place in the Outpatient Clinic Department of Pennington Biomedical. The testing this day includes the following procedures:

- Anthropometric Measurements – (body weight, waist and hip circumference, and bioelectrical impedance)
- Psychological and Behavioral Questionnaires
- Females of child-bearing potential will have a urine pregnancy test
- MRI/fMRI – fasting and fed state
- Treatment consumption – fed state fMRI
- Adherence check

All participants need to come in within \pm 2 days of their scheduled visit date.

Phone calls, text messages and email are also permissible by the adherence coach as adherence checks during the dietary intervention. Also adherence coaches can request remote motoring i.e. pictures of study foods.

Study Procedures:

As previously stated, the foods listed above will be provided to participants with instructions to consume one serving per day. If they happen to skip a day, participants will be instructed to consume the treatment on the following day on top of their normal daily provision. The energy content of food provision in the SSB and solid groups will be 240 kcal/day (SSB and solid groups will be isocaloric). Participants will receive no instructions for other dietary modifications; i.e., they will not be told to modify what or how much other food they consume.

fMRI: Reward Activation

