Pulse oximeter: The pulse oximeter is an optical sensor that clips onto one of the fingers of either hand or toes of either foot. It shines a light through the skin to gather proxy measures of blood oxygenation while the scan is being collected. Dynamic MRI data, especially functional and perfusion MRI, is commonly corrected by regressing the time course of peripheral blood oxygenation out of the raw time series data acquired. The sensor attaches snugly to the finger but generally does not pinch or cut off the flow of blood.

Image and video display screen: Participants view images projected from a screen through a mirror mounted on the MRI head coil. Commonly deployed experimental paradigms display images during fMRI data collection to assess responses of the brain to various visual stimuli.

Headphones: MR-safe headphones are worn inside the head coil and over the ears.

Button boxes: In functional MRI experiments, participants are commonly asked to indicate responses to questions about the images, sounds, smells, and tastes exposed to them in the scanner by pressing buttons on button boxes placed in their hands.

MR scanning

The scanner technician runs a series of sequence acquisitions, each of which quantify a different aspect of tissue structure and function, or covers a slightly different portion of the anatomy. Each sequence acquisition emits a series of buzzing or grinding noises over the course of 1 to 10 minutes while data is acquired. Before each sequence acquisition, the technician communicates with the participant via a speaker and microphone inside the scanner bore; the participant is asked about his/her comfort and is reminded to lie perfectly still during the subsequent sequence acquisition. The technician has an unobstructed view of the participant to identify movement during acquisition or other signs of discomfort. After scanning, the participant is removed from the scanner tube and assisted out of the scanner suite.

Statistical analysis. The study will use an intent to treat approach. Following evaluation of data normality, a mixed model ANOVA will be used to test if change on the outcome variables differed between treatment and control across time. LS Means will also test if change from baseline was significantly different from 0. Fixed effects will include age and sex.

Power Analysis:

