Since this is a pilot and feasibility study, power calculations have not been performed. This study will allow us to obtain crucial feasibility data as well as data to perform future power calculations for a larger grant.

Data Banking

The PIs and co-investigators will have access to the data for future analysis and they may be shared with outside investigators.

Data Management

The data management will be conducted by the Pennington Biomedical Research Computing Group. There will be limited access to all data including locked cabinets for paper files and password protected computers for electronic data. Identifiers will be kept separate from the data.

Provisions to Monitor the Data to Ensure the Safety of Subjects

The Principal Investigators (PIs) are responsible for monitoring the data, assuring protocol compliance and conducting safety reviews at the specified frequency [quarterly]. During the review process, the Principal Investigators will evaluate whether the study should continue unchanged, requires modification/amendment or should close to enrollment.

The Principal Investigators or the Institutional Review Board (IRB) or have the authority to stop or suspend the study or require modifications.

This protocol presents minimal risks to subjects, and adverse events or other problems are not anticipated. In the unlikely event that such events occur, the PIs are responsible for reporting to the IRB and any appropriate funding and regulatory agencies any serious, unanticipated and related adverse events or unanticipated problems involving risks to subjects or others. The investigators will apprise fellow investigators and study personnel of all adverse events that occur during the conduct of this research project. The investigator will meet this obligation through email as they are reviewed by the Principal Investigators. The study's Research Monitor(s) and decision-making bodies will be informed of serious adverse events within 10 working days of the event becoming known to the Principal Investigators. If there are unanticipated problems involving risks to subjects or others, these should be reported to the IRB per HRPP Policy 8.0.

The sub-investigator, [name], will review adverse events.

Withdrawal of Subjects

Subjects may be withdrawn from the study if he/she misses study visits or food provision and will be notified of their withdrawal via telephone or mail.

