If a subject voluntarily withdraws from the study, no additional data will be collected and they will be considered drop outs in the study.

Risks to Subjects

This study does not involve major risk to study participants.

- **Fasting for 10 hours:** There is a possibility that fasting for 10 hours may make you feel nauseous.
- **Self-reported Questionnaires:** There are no anticipated risks from completing self-report questionnaires. Due to the sensitive nature of the questionnaires, you may skip any questions that you do not wish to answer.
- **Bioelectrical Impedance Analysis (BIA) Measurement:** You will be asked to change into a gown and to remove all footwear and socks/stockings. Once changed and barefoot, you will be asked to stand on a scale (similar to a large gym scale), and you may be asked to hold on to hand electrodes on each side of the scale. You will be asked to step off of the scale once the measurement is complete (less than one minute).

- There is no risk associated with the BIA measurement. **However, subjects with medical implants such as a pacemaker or metal joint replacements cannot be measured on the machine.**
- **Weight Gain:** There is a possible chance that the Calories will slightly increase body weight.
- **Brain MRI:** This scan is performed to measure the size of your brain and lasts approximately ten minutes. You will change into a hospital gown and remove all objects containing metal from your body. During the scan, you will lie on your back on the scanner table with your head in a cradle. The scanner table will then move you into the magnet. During the scan, you will hear loud tapping noises. You will be given headphones for protection from the scanner noise and can listen to music during the scan if desired. You will also be given a call button should you need the MRI tech during the exam. This scan is for research purposes only and not for diagnostic treatment.
 - **MRI Risks:**

There are no known biological risks associated with magnetic resonance scanning. It has been used routinely for over 20 years. It produces side effects in very few situations. Those situations include:

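### Intent-to-treat is promised, but no Week 4 or exit weight is planned for participants whom staff withdraw

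*Protocol*

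**What the plan says.** Four parts of the protocol bear on this.

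- **Endpoint (Study Endpoints):** "The primary study endpoints are feasibility and change in body weight".
- **Analysis set (Statistical analysis):** "The study will use an intent to treat approach", with a mixed model ANOVA for change and a test of each change from baseline against zero.
- **Timing of weight (Table 1):** after screening, the row that begins "Anthropometrics (body weight, waist and hip circumference, and bioelectrical impedance" is marked at Week 0 and Week 4 only. The Week 1, 2 and 3 visit lists contain an adherence check and "1 week supply of study product dispensed", but no weighing.
- **Withdrawal (Withdrawal of Subjects):** "Subjects may be withdrawn from the study if he/she misses study visits or food provision". Such participants "will be notified of their withdrawal via telephone or mail", and nothing further is described for them. A separate sentence covers people who leave by choice: "If a subject voluntarily withdraws from the study, no additional data will be collected and they will be considered drop outs in the study". No equivalent stop on data collection is stated for staff withdrawal.

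**The concern.** The staff rule removes a randomised participant from the study, not only from the study food, and its triggers are markers of poor attendance or adherence. Because weight is next measured at Week 4, anyone withdrawn earlier has a baseline weight and no planned outcome.

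The participants lost this way have probably eaten less of the 240 kcal/day product, so the loss is plausibly related to weight change. If they gain less than those who stay, the within-arm gain is overstated, which is the direction that the protocol hypothesises. If withdrawal differs between the drink and the solid food, the between-arm contrast is biased, in either direction. The pilot is also meant to supply data for later power calculations, so a completers' estimate could be carried forward as if it described everyone randomised.

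An analysis plan can choose how to treat a missing weight, but it cannot recover one that was never taken. The protocol is therefore the place to settle this.

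**Working it through.** The protocol gives no withdrawal rate, SD or power figure, so there is no stated number to reproduce. What follows is an illustration.

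**From the protocol:** 240 kcal/day; 10 participants per arm; one week of product dispensed at each of Weeks 0 to 3. Someone who misses the Week 1, 2 or 3 visit has thus been given 7, 14 or 21 servings.

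**Assumed:** 7,700 kcal per kg; no compensation; 28 servings eaten by those who stay; only the dispensed servings eaten by those withdrawn; withdrawal of 10%, 20% or 30% of an arm (1, 2 or 3 of 10).

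**Step 1: expected gain.** Stayers: 240 × 28 / 7,700 = 0.873 kg. Withdrawn after 7, 14 or 21 servings: 0.218, 0.436 or 0.655 kg. The gap *d* to stayers is 0.655, 0.436 or 0.218 kg.

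**Step 2: within-arm overstatement = p × d (kg).**

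| Withdrawn (p) | after 7 servings | after 14 | after 21 |
|---|---|---|---|
| 10% | 0.065 | 0.044 | 0.022 |
| 20% | 0.131 | 0.087 | 0.044 |
| 30% | 0.196 | 0.131 | 0.065 |

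Relative to the mean in all randomised, this is 3-8% at 10% withdrawal and 8-29% at 30%.

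**Step 3: between-arm bias = (p2 − p1) × d**, with the same *d* in both arms.
- 10% against 30%: 0.131, 0.087 or 0.044 kg.
- 0% against 30%: 0.196, 0.131 or 0.065 kg.
- Equal withdrawal at similar times: zero.

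With 50% compensation every figure in steps 1 to 3 expressed in kg halves, so the largest bias is about 0.10 kg.

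**Step 4: comparison with precision.** With all 20 followed, the two-sample 95% half-width is t(0.975, 18) × √(2/10) = 2.101 × 0.447 = 0.940 SD. For an assumed SD of change of 0.5, 1 or 1.5 kg this is 0.47, 0.94 or 1.41 kg. The largest between-arm bias, 0.196 kg, is 42%, 21% or 14% of that. With 10 against 7 followed, the half-width is 1.050 SD and the shares are about 37%, 19% and 12%.

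**Step 5: can the mixed model recover it?** Two simulations were run.
- One arm of 10 (20,000 runs; assumed baseline SD 15 kg, SD of change 1 kg), with three withdrawn after 7 servings: mean gain was 0.678 kg in all randomised, 0.873 kg in completers, and 0.874 kg when Week 4 was predicted from Week 0 weight.
- Thirty two-arm trials (assumed baseline SD 15 kg, SD of change 1.2 kg), with 4 of 20 lacking Week 4: the mixed-model group-by-time estimate differed from the completers-only difference by at most about 0.02 kg.

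Keeping the baseline record in the model therefore yields practically the completers' answer.

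**The case against.** The strongest reply is that the protocol is silent here rather than contradictory. The rule is permissive, nothing forbids a weight after staff withdrawal, and harm requires three things: the rule is used, no weight is taken, and the withdrawn gain differently. The protocol also makes use of the rule less likely. A skipped serving is made up the next day, visits have a 2-day window, "Phone calls, text messages and email are also permissible by the adherence coach as adherence checks during the dietary intervention", and $125 of the $230 maximum is paid for Week 4. All this stands, and it is why the point is conditional and minor. It does not supply a weight once the rule has been used.

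Further objections deserve an answer.

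- **Attribution.** People who miss visits may miss Week 4 anyway, so the figures above are an upper bound on what the rule itself causes. This stands; the share due to the rule cannot be calculated from the protocol.
- **The model.** A mixed model is unbiased if missingness depends only on arm, baseline weight, age and sex, and the simulations drew gain unrelated to baseline weight. That is fair, but the trigger here is attendance and adherence. Returned containers and self-report could inform an imputation, but the stated analysis does not use them, and they would help only if adherence predicts gain.
- **Extreme inputs.** Zero compensation is the upper case, and the Background itself cites a study in which weight gain fell well short of that. The 0.20 kg between-arm figure also needs all three withdrawals to fall in one arm after 7 servings. Both points stand, and the ranges above show the milder cases.
- **Voluntary withdrawal.** The remedy does not reach these participants. That is true, but it does not remove the gain for those whom staff withdraw.

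**Conclusion.** The concern holds, as a minor one. If staff use the withdrawal rule and no later weight is taken, the weight result describes those who kept attending or adhering, not all randomised, and the planned model will not correct this.

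Under the stated assumptions the within-arm overstatement is 0.02-0.20 kg, with a between-arm bias of at most 0.20 kg in the scenarios considered. The bias is zero if nobody is withdrawn, if a Week 4 weight is taken anyway, or if the withdrawn gain the same as the rest. In a 20-person pilot this is well inside the sampling uncertainty. It is nevertheless a systematic error that is cheap to avoid and cannot be repaired afterwards. Withdrawal rates, kcal per kg, compensation, servings eaten and SDs are all assumptions.

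**What to change.** Leave the study-food rules, the discretion to withdraw and the voluntary-withdrawal text as they are. Add to Withdrawal of Subjects:

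> For any randomised participant withdrawn by staff who has not withdrawn consent to data collection, a fasting weight at the scheduled Week 4 time will be sought and included in the intent-to-treat analysis.

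Report staff withdrawals by arm with the reason; these counts also serve the feasibility endpoint. If the sentence is not adopted, describe the weight analysis as completers only.

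The cost is one sentence and, at 10-30% withdrawal, 1-3 extra weigh-ins per arm. Whether a weight-only visit is paid, and whether the consent wording covers it, would need settling. Some withdrawn participants will still not attend, so the gap shrinks but may not close, and the reported gain may be smaller.
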